12.1 Interventions being assessed

Patients recruited to the pilot feasibility trial who agree to be randomised to either ablation or active surveillance will undergo routine biopsy of the renal tumour to confirm that it is a cancerous growth. At centres where this biopsy is not routine, the participant must consent to the biopsy and the study prior to the biopsy being performed. Details of the biopsy can be seen in section 14.1.5 of the protocol.

Patients randomised to the ablation arm will undergo second compulsory biopsy six months after treatment. This will be conducted under ultrasound or CT guidance using local analgesia.

The ablation methods used will depend on what expertise is available at study sites. Sites will offer only one form of ablation. The permitted ablation methods will include Radiofrequency ablation (RFA), cryoablation (CRA) and microwave ablation (MWA).

The paragraphs below give more detail about the ablative procedures and active surveillance.

Radiofrequency ablation (RFA): Radiofrequency probes are carefully positioned into the renal mass lesion percutaneously by image guidance (usually using CT) and laparoscopically by direct vision.

RF probes deliver localized monopolar currents at 'radiofrequency' (400-500kHz) to generate frictional heating in the adjacent tissue. Through direct and conductive heating, this achieves temperatures of up to 105°C. Tissue destruction occurs by protein denaturation, cell destruction and coagulative necrosis in a sometimes ill-defined sphere around the probe tip. This ablation zone can be compromised by tissue perfusion-mediated cooling and larger adjacent flowing vessels but can usually achieve ablation zones of up to 4-5cm in diameter. Sometimes probes may be re-positioned to achieve the required ablation volume.

The procedure is well-tolerated but now more usually performed under general anaesthesia to achieve optimal probe positioning and outcomes. Where necessary, adjacent bowel or other structures are displaced by contrast-tinted 5% dextrose for retroperitoneal hydrodissection (however, carbon dioxide can also be used). Therapeutic outcomes are confirmed by contrast-enhanced CT or MR within 3 month post-ablation⁴⁰.

Cryoablation (CRA): Cryoprobes are applied laparoscopically or percutaneously by image guidance. Localised tip temperatures of -150°C and lower can be achieved by utilising the phase change of compressed argon gas delivered through multiple closed needle applicators, arranged in a format to create a confluent 'therapeutic' ice ball. Within the induced ice ball a range of tissue-lethal temperatures are achieved. At the -30°C isotherm a double freeze-thaw cycle is believed to yield uniform cell death. Tissue destruction is achieved through disruptive cell necrosis and microvascular injury.

Microwave ablation (MWA): Microwave ablation is very similar to RFA. A similar sized needle/probe is inserted into the lesion under imaging guidance exactly as for RFA. The microwave probe causes heating of the tissue by heating the water molecules within it achieving similar temperatures to RFA causing cell destruction and coagulative necrosis.

Active surveillance: Patients randomised to active surveillance will be put on the following schedule:

Urea and Electrolytes including eGFR (glomerular filtration rate), MDRD (Modification of Diet in Renal Disease) equation if performed clinically (there is no need to report this to the study team), and 6 month CT of the abdomen. Participants will undergo CT scan of the abdomen (phasing and sequencing details to be determined by site as per their local practice).

Tumour volume would be calculated from the 3-dimensional diameters using the formula to calculate an ellipsoid volume:

Volume = 0.5326 x (diameter 1) x (diameter 2) x (diameter 3)

If there is progression of the growth rate or the size of the tumour in patients on the active surveillance arm, ablation or partial nephrectomy will be offered depending on the facilities available in the participating centre.

Progression will be considered to have occurred when either

- (i) Growth rate exceeds 2.5mm/six months
- (ii) There is a doubling of tumour volume by 6 months

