14.1 Patient Assessments / Data Collection

14.1.1 Screening and Baseline visit (for all participants)

Pre-Screening & Screening

- PIS provided
- Eligibility criteria checked

Baseline

Written informed consent will be taken. If not already done, arrangements will then be made for a biopsy procedure to take place before randomisation is performed.

The baseline visit will involve collection and retrospective collation of the following data:

- Demographics (age, gender)
- Medical history
- Blood test and urinalysis will be taken as per local policy. There is no requirement to report these to the study team or record them on the study eCRF.
- SF-36
- STAI
- FACT-G
- Biopsy results are to be recorded in the baseline eCRF – to document relevant details and presence of cancerous growth. If a routine diagnostic biopsy is NOT standard care at site, consent for the biopsy and the study MUST be given prior to the biopsy procedure.
- Tumour size and volume are to be recorded from routine CT/MRI imaging already obtained during diagnosis of tumour. Size is to be recorded in 3 planes of measurement. Size is to be recorded in 3 planes of measurement. Volume = $0.5236 \times (\text{diameter } 1) \times (\text{diameter } 2) \times (\text{diameter } 3)$. The volume calculation is not to be completed by site.
- Confirmation must be recorded in the eCRF that study inclusion criteria are fulfilled and no exclusion criteria apply.

Randomisation should occur after the baseline visit and after review of biopsy results and checking of inclusion/exclusion criteria. Randomisation should not occur if the biopsy shows a non-cancerous result.

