14.1.3 Three Month Follow up (for all participants)

The three month follow up will take place at 3 months (+/-14days) after the treatment date for patients in the ablation arm.

The three month follow up will take place at 3 months post randomisation (+/-14days) in the active surveillance arm.

At the 3 month, follow up the following will be administered to all patients:

- Blood test and urinalysis will be taken as per local policy. There is no requirement to report these to the study team or record them on the study eCRF.
- SF-36
- STAI
- FACT-G

Imaging results will need to be obtained in order to document any changes in tumour progression as follows:

- For patients receiving ablation (using any of the methods) data is to be captured from a routine CT/MRI scan of the abdomen performed within 3 months of the ablative procedure
- For patients receiving active surveillance: a 3 month post randomisation scan of the abdomen is optional depending on routine practice at site.

The imaging will allow capture of the following data on the CRF:

- Tumour size and volume. Size is to be recorded in 3 planes of measurement. Size is to be recorded in 3 planes of measurement. $\text{Volume} = 0.5326 \times (\text{diameter } 1) \times (\text{diameter } 2) \times (\text{diameter } 3)$. The volume calculation is not to be completed by site.
- Confirmation of any progression of the tumour.

The following additional data will also be captured for all patients:

- Any changes in treatment plan (eg switching from active surveillance to ablation or surgical excision). Dates and times and types of procedures to be recorded. Reasons for a switch in treatment (i.e. reason for cross-over).
- Complications of treatment and adverse events will be recorded
- Administration of health economics questionnaire: PCQ (Part A)

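### The ellipsoid volume constant is misprinted as 0.5326 in sections 12.1 and 14.1.3; sections 14.1.1 and 14.1.4 give the correct 0.5236 (minor)

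*Protocol*

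**What the plan says.** The protocol states the volume formula four times, with two different constants.

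- Section 12.1, active surveillance: "Tumour volume would be calculated from the 3-dimensional diameters using the formula to calculate an ellipsoid volume", followed by "Volume = 0.5326 x (diameter 1) x (diameter 2) x (diameter 3"). The constant is 0.5326.
- Section 14.1.1, baseline: "Volume = $0.5236" (the dollar sign is a typesetting mark, not part of the figure). The constant is 0.5236.
- Section 14.1.3, three months: 0.5326.
- Section 14.1.4, six months: 0.5236.

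Section 12.1 then names two alternative progression criteria for the surveillance arm: "Growth rate exceeds 2.5mm/six months" and "There is a doubling of tumour volume by 6 months". Either one leads to an offer of further treatment.

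Sections 14.1.1, 14.1.3 and 14.1.4 take the calculation away from the centres: "The volume calculation is not to be completed by site". No section says which constant prevails.

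**The concern.** Two constants for one geometric formula cannot both be right, and the formula decides which is. A printing slip matters more than usual here for two reasons. Volume is a recorded quantity that enters a progression criterion, and the wrong constant stands directly above that criterion. Also, since sites do not compute volume, someone else must program it, and the protocol is the natural specification. A programmer who followed section 14 visit by visit would use 0.5236, then 0.5326, then 0.5236, which puts a change into the series that does not come from the diameters.

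**Working it through.** **Which constant is right.** An ellipsoid with diameters d1, d2, d3 has volume (4/3) × pi × (d1/2) × (d2/2) × (d3/2) = (pi/6) × d1 × d2 × d3, and pi/6 = 0.523599.

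- 0.5236 (14.1.1, 14.1.4) reproduces pi/6 to four decimals.
- 0.5326 (12.1, 14.1.3) does not: 0.5326/0.523599 = 1.0172, so it is 1.72% too high.

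**Section 14 applied as printed, diameters unchanged.**

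| Interval | Ratio of constants | Apparent change |
|---|---|---|
| Baseline to 3 months | 0.5326/0.5236 = 1.0172 | +1.72% |
| 3 to 6 months | 0.5236/0.5326 = 0.9831 | −1.69% |
| Baseline to 6 months | 0.5236/0.5236 = 1 | 0% |

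**Absolute size.** The excess for a sphere is (0.5326 − 0.5236) × d³ = 0.009 × d³: 0.07 cm³ at 2 cm, 0.24 cm³ at 3 cm and 0.53 cm³ at 3.9 cm, just under the 4 cm entry limit. In diameter terms, the cube root of 1.0172 is 1.0057, or about 0.17 mm on a 3 cm tumour.

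**Who is affected.** In the ablation arm, 14.1.3 calls for data from a scan within 3 months of the procedure. In the other arm: "For patients receiving active surveillance: a 3 month post randomisation scan of the abdomen is optional depending on routine practice at site". The inflated 3-month volume therefore arises mainly in the ablation arm, with a planned 30 patients (section 16.1), plus any surveillance patient who happens to have a 3-month scan.

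**The doubling criterion.** Under section 14 the 6-month to baseline ratio uses 0.5236 twice, so the constant cancels. It also cancels if 0.5326 is used at both visits. Only mixed constants shift the threshold: with baseline at 0.5236 and follow-up at 0.5326, doubling is declared at a true ratio of 2 × 0.5236/0.5326 = 1.966.

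**Would that change a progression call?** Assume all three diameters grow in the same proportion.

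- A true doubling needs a diameter increase of 2^(1/3) − 1 = 26.0%, which is 7.80 mm for a 3 cm tumour.
- A ratio of 1.966 needs 25.3%, which is 7.58 mm.
- Both far exceed the 2.5 mm in the other criterion, which does not use the constant. The size at which 2.5 mm equals doubling is 2.5/0.2599 = 9.6 mm (2.5/0.2528 = 9.9 mm with mixed constants). Above that size the diameter criterion is met first.

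**The case against.** The strongest reply is that this is a typographical slip without consequence. The two visits that define the 6-month ratio agree with each other and are correct. Sites never apply the formula, so one derivation with one constant removes the artefact. The diameter criterion usually acts first. Volume is not among the outcome measures listed in section 9 or the estimates and success criteria listed in section 16.2, which concern recruitment, retention, complications, outcome collection and the spread of quality-of-life scores. All of this stands, and it limits the severity. It does not remove the error: a formula in force is wrong in two places, and following 14.1.3 literally gives a wrong volume.

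A reader might infer two stronger points that the documents do not support.

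- *The doubling test is loosened to 1.966.* For the 6-month scan this requires the constant from 12.1 at follow-up and from 14.1.1 at baseline, with 14.1.4 ignored. Section 12.1 gives one general formula tied to no visit; read as a general rule, it covers baseline as well and the ratio is again unaffected. The mix could occur if an optional 3-month surveillance volume were tested against baseline, but under uniform growth in a tumour above about 9.9 mm the diameter criterion would already be met.
- *Growth is misstated by about a fifth.* Take an assumed 2.6 cm tumour growing at the mean of 0.28 cm a year cited in section 7. The true 3-month change is (2.67/2.60)³ − 1 = 8.3% and would read 1.0830 × 1.0172 − 1 = 10.2%. The arithmetic is right, but it applies untreated growth to a scan that is optional in the untreated arm. In the ablation arm, where the scan is routine, natural growth does not apply and the doubling rule is not used.

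**Conclusion.** The error is certain and its effect is small. The constant 0.5326 in 12.1 and 14.1.3 is wrong, and 0.5236 in 14.1.1 and 14.1.4 is right. Literal use of section 14 makes 3-month volumes 1.72% too high and produces a spurious rise and fall of 1.7%, chiefly in the ablation arm. If 0.5326 were instead used throughout, ratios would be correct and only absolute volumes would be 1.72% too high.

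The conclusion that few if any progression calls would change rests on roughly uniform growth and tumours above about 1 cm; markedly uneven growth could differ. The protocol does not show how the derivation was programmed, so the artefact is a risk rather than an established fault in the data. The issue is minor.

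**What to change.** Replace 0.5326 with 0.5236 (pi/6) in sections 12.1 and 14.1.3, and add one sentence stating that the same constant applies at every visit. Check that the volume derivation uses it, and re-derive any volume found to have used 0.5326; the recorded diameters are enough for this. The cost is two corrected lines, one added sentence and one derivation check. The change concerns only the geometric constant and leaves the progression criteria as they are.

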12.2 Routine imaging for monitoring disease progression and recurrence

All patients will also undertake Computerised Tomography (CT) scans to assess for disease progression and recurrence.

CT scans of the abdomen will take place within 3 and 6 months post-treatment for patients undergoing radiofrequency ablation, cryoablation or microwave ablation and at 6 months for patients having active surveillance. If sites happen to have any routine scan results available for active surveillance patients at 3 months post-randomisation then the study team would be interested in receiving these data – however, this is optional depending on local practice. Sites also have the flexibility to perform any other scans which are deemed clinically necessary/standard practice at site. The scan sequencing will be determined by the local site.

We would like a record of the number of scans performed by site clinically on each participant in addition to the 3 and 6 month scans reported for the study.

Magnetic Resonance Imaging (MRI) scans may be used as an alternative to CT scans if the normal practice within a site is to undertake MRI scans as part of routine clinical practice.

12.3 Qualitative Interviews in a sub-set of patients for the Parallel Qualitative Component

In parallel to the pilot feasibility trial, we will explore the barriers and facilitators to participation in the trial. We believe it is important to do so with patients approached to participate in a real rather than hypothetical trial since what people say they will do is often different to how they will react when faced with a real decision.

In terms assessing the feasibility of a future definitive trial we wish to interview a mix of patients taking part in this pilot feasibility trial in order to address and find solutions to issues around recruitment and retention. We will conduct in-depth face to face interviews with patients who:

- consent (5 in ablation and 5 in active surveillance group)
- decline (5)
- withdraw following randomisation (5)

In the interviews we will explore patients' views on: aspects of the informed consent process including method of approach, time to make a decision, the content and amount of written

and verbal trial information and their understanding of it and what was required of them in the trial; reasons they declined/agreed to participate; under what circumstances would they participate/not participate. We will not formally assess understanding but will ask patients what they believe to be the purpose of the trial, what the two 'treatment' arms involve, what are the risks and benefits and what is required of participants. From this we will be able to determine whether the verbal and written trial information is effective in informing patients and detect areas that need to be improved in any future trial.

With the group who do not decline or withdraw following randomisation we will also explore their experiences of participating in the trial, including their views on the arm they were randomised to, whether they underwent any further treatment and completion of the outcome measures (SF36, STAI, FACT-G). These interviews will be conducted after the final follow up (treatment plus 6 months). If possible we will also interview any patients who drop out of the trial between treatment and final follow up to explore their reasons for doing so.

12.4 Clinician Interviews for the Parallel Qualitative Component

We will interview clinicians about their views on:

- participating and recruiting to the trial
- the trial patient information
- instances where they were unwilling or unhappy to recruit certain eligible patients to the trial
- explore why and whether they consider there has been a change in their clinical equipoise from first agreeing to be part of the trial to the point where they were recruiting patients.

During the set up phase we will consult with clinicians participating in the pilot trial about how best to capture cases where they were unwilling to recruit; for example whether it would be appropriate for them to briefly document these cases which can then be referred to during their interviews.

Wherever possible we will conduct face to face interviews with clinicians but envisage some may have to be carried out over the telephone in some sites or if it is difficult for them to find the time to meet with the researcher.

13. Randomisation and Blinding

13.1 Randomisation

When all eligibility checks have been made and written informed consent has been given, participants in the pilot feasibility trial will be randomised on a 1:1 ratio (stratified by centre) to either active surveillance or ablative treatment (radio frequency ablation or cryotherapy ablation or microwave ablation). The exact nature of ablation (RFA or CRA or MWA) would depend on the equipment and expertise available in the participating centre; currently, centres have tended to develop expertise in either cryotherapy, microwave or radiofrequency ablation; centres will therefore offer only one form of ablation (the one in which they have expertise).

Randomisation will be undertaken using the central web based randomisation service available in the Newcastle Clinical Trials Unit. The PI at site, or individual with delegate authority, will access the web-based randomisation system. Patient screening ID, initials and centre (the stratifying variable) will be entered into the web-based system, which will return the allocation status (successful randomisation will be followed up by an automated confirmatory email to the site and relevant Newcastle Clinical Trials Unit staff).

Participants will then be informed of their allocated treatment group by the site PI or delegated individual following randomisation.

Following allocation the site will

1. Organise procedure date for those allocated for ablative treatment
2. Organise active surveillance protocol for those allocated to active surveillance arm

Contact details for Randomisation:

Randomisation service website: <http://apps.ncl.ac.uk/random/>
(Available 24 hours a day)

Queries about the randomisation system can also be addressed to:
[contact] (normal office hours)

13.2 Blinding

This is a feasibility study with primary outcome listed as recruitment and retention rates and qualitatively in terms of the patients' experiences and understanding of the randomisation process and treatment options. Due to this, it will not be necessary to blind staff to the treatment allocated to patients for the follow up assessments.

The baseline data capture assessments will however be completed by research nurses before randomisation in order to reduce any bias in terms of patient attitude to allocated treatment affecting baseline data.

14. Study Data

14.1 Patient Assessments / Data Collection

14.1.1 Screening and Baseline visit (for all participants)

Pre-Screening & Screening

- PIS provided
- Eligibility criteria checked

Baseline

Written informed consent will be taken. If not already done, arrangements will then be made for a biopsy procedure to take place before randomisation is performed.

The baseline visit will involve collection and retrospective collation of the following data:

- Demographics (age, gender)
- Medical history
- Blood test and urinalysis will be taken as per local policy. There is no requirement to report these to the study team or record them on the study eCRF.
- SF-36
- STAI
- FACT-G
- Biopsy results are to be recorded in the baseline eCRF – to document relevant details and presence of cancerous growth. If a routine diagnostic biopsy is NOT standard care at site, consent for the biopsy and the study MUST be given prior to the biopsy procedure.
- Tumour size and volume are to be recorded from routine CT/MRI imaging already obtained during diagnosis of tumour. Size is to be recorded in 3 planes of measurement. Size is to be recorded in 3 planes of measurement. Volume = $0.5236 \times (\text{diameter } 1) \times (\text{diameter } 2) \times (\text{diameter } 3)$. The volume calculation is not to be completed by site.
- Confirmation must be recorded in the eCRF that study inclusion criteria are fulfilled and no exclusion criteria apply.

Randomisation should occur after the baseline visit and after review of biopsy results and checking of inclusion/exclusion criteria. Randomisation should not occur if the biopsy shows a non-cancerous result.

14.1.2 Treatment (for participants randomised to Ablation)

Our expectation would be that ablative treatment will be ideally provided within 1 month of randomisation (+/-14 days) or as per standard national NHS protocols.

The following data will be copied into the study eCRFs from NHS medical records in relation to the provision of ablative treatment:

- Type of ablative treatment provided and date/time.
- Whether the treatment was provided as per the randomisation allocation.

- Any reason(s) for not providing treatment as per the randomisation allocation.
- Any alternative treatments provided (eg. surgical excision as an alternative).
- Complications of treatment and adverse events will be recorded.

14.1.3 Three Month Follow up (for all participants)

The three month follow up will take place at 3 months (+/-14days) after the treatment date for patients in the ablation arm.

The three month follow up will take place at 3 months post randomisation (+/-14days) in the active surveillance arm.

At the 3 month, follow up the following will be administered to all patients:

- Blood test and urinalysis will be taken as per local policy. There is no requirement to report these to the study team or record them on the study eCRF.
- SF-36
- STAI
- FACT-G

Imaging results will need to be obtained in order to document any changes in tumour progression as follows:

- For patients receiving ablation (using any of the methods) data is to be captured from a routine CT/MRI scan of the abdomen performed within 3 months of the ablative procedure
- For patients receiving active surveillance: a 3 month post randomisation scan of the abdomen is optional depending on routine practice at site.

The imaging will allow capture of the following data on the CRF:

- Tumour size and volume. Size is to be recorded in 3 planes of measurement. Size is to be recorded in 3 planes of measurement. $\text{Volume} = 0.5326 \times (\text{diameter } 1) \times (\text{diameter } 2) \times (\text{diameter } 3)$. The volume calculation is not to be completed by site.
- Confirmation of any progression of the tumour.

The following additional data will also be captured for all patients:

- Any changes in treatment plan (eg switching from active surveillance to ablation or surgical excision). Dates and times and types of procedures to be recorded. Reasons for a switch in treatment (i.e. reason for cross-over).
- Complications of treatment and adverse events will be recorded
- Administration of health economics questionnaire: PCQ (Part A)

